5 STUDY ENROLLMENT AND WITHDRAWAL

The total target sample size for enrollment in Phase 1 is 125 participants and in Phase 2, 100 participants (50 participants per arm). A higher enrollment is expected for Phase 1 than Phase 2 to account for some participants being deemed ineligible to proceed with Phase 2.

Potential participants are identified through upcoming cardiology clinic rosters who meet the age (15-25 years of age) and diagnosis (moderate to complex CHD³) criteria. Study personnel check the patient's medical record to verify eligibility. If a patient appears to be eligible, study staff confirm with the attending cardiologist that no additional reason/s preclude the adolescent from participating, including limitations to engaging in MVPA. Next, the patient, or if an adolescent, the patient's caregiver(s) (or their legal guardian of record), is sent a letter from the attending cardiologist, notifying them about the study and that study personnel will be in contact. An "opt out" phone number is provided so that the caregiver(s) can call and leave a message if they do not wish to be contacted. Approximately 1 week later, if no message was received, caregiver(s) are called by study personnel. During the phone conversation, the objectives and primary components of the study are discussed. If a patient and/or caregiver are interested, verbal consent/assent (if <18 years of age) is obtained for completing online questionnaires and the exercise stress test at NCH is scheduled. During the stress test visit, written consent/assent for the stress test and accelerometer assessment is obtained. If a patient and/or a caregiver cannot be reached via phone, they are approached during their clinic appointment in person.

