6.4 Interim Assessment (between weeks 8-12)

Participants in both arms are asked to complete an interim assessment (between weeks 8-12), which includes:

Interim online questionnaire: Participants are asked to complete the same questionnaire that was completed at Baseline, with the exception of those in the comparison arm receiving questions about changes to their health since Baseline.

- Benefits of PA⁵⁰

- Subjective Norms survey⁵¹

- Social Support for Exercise survey⁵²

- Barriers to Exercise survey⁵³

- Self-Efficacy for Exercise Scale⁵⁴

- Patient-Reported Outcomes Measurement Information System⁴⁵⁻⁴⁷

- International Physical Activity Questionnaire^{48,49}

- Cardiac Anxiety Questionnaire⁵⁵

- Changes in Health

MVPA and SB: Participants wear an accelerometer again for the same period (7 days) as the Baseline assessment and complete self-monitoring PA logs in the case they cannot wear the accelerometer (e.g. swimming).

Compensation: Participants are compensated \$50 for completion of the interim assessment survey and wearing the accelerometer for at least 4 days (1 weekend day, 3 weekdays), for at least 10 hours per day.

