7.6 Study Hypotheses

Hypothesis 1: Participants are hypothesized to rate the intervention as not burdensome, easy to access, and appealing. Additionally, recruitment and retention rates are predicted to be $\geq 75\%$.

Hypothesis 2: Participants in the treatment arm will (A) increase MVPA relative to those in the comparison arm at post-intervention, (B) decrease SB relative to those in the comparison arm, and (C) demonstrate an increase in VO_{2max} at post-intervention relative to those in the comparison arm.

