7.7 Sample Size Considerations

A sample size of $n=50$ per group will provide 80% power to detect a large effect size⁵⁹ for the standardized mean difference, still allowing for possible detection of a medium effect size ($d=.6$) with 55% power. Effect sizes from relevant studies examining change in MVPA range from large ($d=.94$; CHD adolescents in a motivational interviewing-style exercise intervention)²⁸ to small ($d=.17$; older adults with cardiovascular risk factors).²² Thus, our primary goal is to estimate an initial effect size for our intervention in our population, with a secondary goal to detect large effect sizes that may exist for study outcomes. However, effect estimation with a relatively small sample size should be interpreted with caution, as it may under or overestimate the sample size.^{60,61}

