7.9 Analysis Plan

Aim 1: Evaluate the feasibility of the intervention.

The mean/median ratings by participants on multiple dimensions of the intervention will be computed. Recruitment rate will be calculated as a percentage of those recruited out of those approached. Percent adherence across sessions will be calculated for those in the intervention arm as the number of sessions attended out of 8. The retention rate will be identified by dividing the number of participants who do not complete the study by the number of participants enrolled.

Verbal responses collected during the focus groups will be transcribed and then coded so that the frequencies of suggestions can be calculated.

Aim 2: Examine preliminary efficacy of the intervention on time spent in MVPA.

First, independent sample t-tests (continuous variables) or chi-square tests (categorical variables) will compare study arms on all variables at baseline, *including biological considerations such as sex and disease status*, to determine if statistically significant differences are present. Only the pre-specified covariates of baseline minutes spent in MVPA and baseline VO_{2max} will be included in the primary analyses.⁶² However, if statistically significant differences are found at baseline, those variables will be examined as covariates in all statistical models of interest in an exploratory fashion.

Second, the following statistical model for repeated measures (RM), based on maximum likelihood estimation, will be employed,⁶³ $y_{it} = \beta_0 + \beta_1 Time_t + \beta_2 Time_t \times Trt_i + \varepsilon_{it}$, where implicitly it is assumed that there is no main effect of Trt_i , y_{it} is minutes in MVPA at time t , $Time_t$ is coded as 0 for baseline and 1 for post-intervention, and the primary effect of interest is β_2 , which is the difference between groups on participants' minutes in MVPA. In this RM model, baseline levels of minutes in MVPA is constrained to have equal means across groups by assuming there is no main effect of the intervention, Trt_i . This constraint yields a statistical test for β_2 analogous to the test of the treatment group main effect per ANCOVA without requiring list-wise deletion to account for missing data. A similar strategy will be taken for analyzing change in SB and VO_{2max} as secondary outcomes.

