Aim 3: Explore mechanisms of change in MVPA and SB, as specified by the Theory of Planned Behavior, including attitudes (i.e., knowledge about and belief in positive outcomes from PA), normative beliefs (i.e., participant-report of family/friend/physician beliefs about and support of PA) and perceived behavioral control (i.e., barriers and efficacy for PA).

Differences between intervention and comparison arm participants on attitudes, normative beliefs and perceived control at the interim assessment will be examined using independent sample t-tests. These variables then will be included in longitudinal mediation models exploring the indirect effects of the intervention on change in behavior as compared to the comparison group on MVPA and SB via the identified mechanisms at the interim assessment. We will use Mplus, which employs bootstrapping to statistically test mediators of the pathway of interest, both individually and simultaneously, to estimate whether one accounts for more variance in the

treatment effect relative to another. We will follow guidelines for testing longitudinal mediation within Cole & Maxwell⁶³ and MacKinnon.⁶⁴ We acknowledge that due to the limited sample size, significant mediation may not be detectable. However, indirect paths nearing significance will have important implications for the future refinement of the intervention by allowing us to focus on the most salient mechanisms of behavior change for the R01 application. Significant Pearson correlations between baseline levels of proposed mechanisms of change and MVPA and SB may also be informative for adjusting the intervention prior to the R01 application to more directly address these factors. Sex will be explored as a potential moderator of intervention effects.

Other Analyses: Relationships between other predictors and study outcomes will also be explored. For example, cardiac-related anxiety, body image disturbance, caregiver perceptions will be examined as possible predictors of participants' willingness to participate in Phase 2 of the study, as well as change in the study outcome variables using linear regression.

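### Aim 3 compares interim mechanism scores by unadjusted t-tests although the same scales are collected at baseline; adjusting for baseline would add precision at no cost

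*Combined protocol and SAP*

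**What the plan says.** The Aim 3 paragraph of Section 7.9 states that differences between the arms on attitudes, normative beliefs and perceived control "at the interim assessment will be examined using independent sample t-tests". It names no baseline covariate. It continues: "These variables then will be included in longitudinal mediation models". The terms of those models are not written out.

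Section 3.2.4 assigns five scales to these constructs: Benefits of PA (attitudes), Subjective Norms and Social Support (norms), and Barriers and Self-Efficacy (perceived control). All five are in the baseline list in Section 6.2 and again in the interim list in Section 6.4, which says: "Participants are asked to complete the same questionnaire that was completed at Baseline".

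For Aim 2, Section 7.9 uses a repeated-measures model with equal baseline means across arms. It describes the resulting test as "analogous to the test of the treatment group main effect per ANCOVA". The same approach is planned for SB and VO2max, but not for the mechanism scores.

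Section 7.9 also has a general rule: "if statistically significant differences are found at baseline, those variables will be examined as covariates in all statistical models of interest". That examination is labelled exploratory.

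**The concern.** The plan collects a baseline value of every mechanism score and then compares the arms on the interim value alone. It recognises the worth of baseline information elsewhere: Section 2.1 argues that stratifying on and adjusting for baseline activity lets the trial detect group differences with fewer participants, and Aim 2 builds this into its model. No reason is given for treating the mechanism scores differently.

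At stake is the precision of the estimated effect of coaching on each mechanism. Aim 3 is meant to inform refinement of the intervention for the next grant application. A less precise arm comparison makes it harder to see which mechanisms moved, and leaves any chance baseline difference in the estimate.

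**Working it through.** **Inputs**
- Sample size: "50 participants per arm" (Section 5), allocated 1:1.
- Significance level: not stated; two-sided 5% assumed.
- Baseline-interim correlation rho of the scales: not stated; 0.3 to 0.7 shown.
- Retention: Section 7.6 says "recruitment and retention rates are predicted to be" at least 75%. Used only as a sensitivity case, 0.75 × 50 = 37.5 per arm.

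**The plan's own power figure.** The documents give no power for Aim 3. The only figures are in Section 7.7, where 50 "per group will provide 80% power to detect a large effect size" and 55% power for d=0.6. Taking large as d=0.8, a two-sided 5% t-test with 50 per group has about 98% power for d=0.8 and 84-85% for d=0.6. The stated figures fit 25 per group (79-81% and 55-56%). That mismatch is a separate matter and neither supports nor weakens this point.

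**Variance.** With n per arm and common standard deviation σ:
- t-test on the interim score: variance of the arm difference = 2σ²/n.
- ANCOVA on the baseline score: approximately 2σ²(1 − rho²)/n.

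The proportional cut is therefore rho². A simulation of 20,000 trials with 50 per arm gave ANCOVA/t-test variance ratios of 0.757 at rho 0.5 (formula 0.75) and 0.515 at rho 0.7 (formula 0.51).

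**Detectable effect and power.** For the t-test with 50 per arm, the normal approximation gives (1.96 + 0.84) × √(2/50) = 0.56; the noncentral t gives 0.566. Under ANCOVA this is multiplied by √(1 − rho²). Power is evaluated at d/√(1 − rho²), with d=0.5 as an illustrative effect.

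| rho | Variance cut | Detectable d at 80% power, n=50 | Power at d=0.5, n=50 | Equivalent n per arm, 50/(1 − rho²) |
|---|---|---|---|---|
| t-test | none | 0.566 | 69.7% | 50 |
| 0.3 | 9% | 0.540 | 73.7% | 54.9 |
| 0.5 | 25% | 0.490 | 81.6% | 66.7 |
| 0.7 | 49% | 0.404 | 93.4% | 98.0 |

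With 37.5 per arm, power at d=0.5 goes from 57.0% (t-test) to 69.4% (rho 0.5) or 84.9% (rho 0.7). This case may be pessimistic: Section 7.9 bases retention on completing the study, and more participants may be available at weeks 8-12.

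**Does the covariate rule recover this?** With 50 per arm, a baseline difference reaches significance at about 1.98 × √(2/50) = 0.40 SD. A difference just below that triggers nothing, yet shifts the expected interim difference by rho × 0.40: about 0.20 SD at rho 0.5 and 0.28 SD at rho 0.7. When the arms are balanced the rule does nothing, whereas ANCOVA still removes the variance that baseline explains.

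**The case against.** The strongest reply is that Aim 3 is labelled exploratory, that an independent-sample t-test is valid and unbiased under randomisation, and that the outcomes the trial is built around already use a baseline-constrained model. All of that stands. It limits the point to a gain in efficiency.

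The plan also has a response to chance imbalance in its covariate rule. It should be weighed, but whether it reaches the t-tests is unclear, and in any case it does not restore precision.

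Four stronger readings are tempting, and the documents do not support them:
- **That the loss is 25-49% as a fact of this trial.** Those figures are rho² for an assumed rho of 0.5 to 0.7. The documents give no correlation for any of the five scales; at rho 0.3 the cut is 9%. The percentage is a share of the variance of the arm difference.
- **That the t-tests decide which mechanisms enter the mediation models.** Section 7.9 says that the variables will be included and states no t-test threshold for entry. It ties the implications for refinement to the indirect paths.
- **That the mediation models ignore baseline.** They are described as longitudinal and concern change in behaviour. The baseline terms are unstated, which is a gap in detail.
- **That the power figures above carry over to mediation.** They describe the arm comparison only. The plan's remark about limited sample size concerns detecting mediation and is not evidence about the t-tests.

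**Conclusion.** The point holds as a free improvement to an exploratory aim. The planned comparison is valid but less precise than the collected data allow. Adjustment would cut the variance of the arm difference by about rho², which is 9%, 25% or 49% for rho of 0.3, 0.5 or 0.7. At 50 per arm the detectable effect falls from d=0.57 to 0.54, 0.49 or 0.40 respectively. These sizes rest on an assumed rho, an assumed two-sided 5% level and equal standard deviations in the arms. The direction does not depend on the exact rho; if rho were near zero, the cost would be about one degree of freedom. The primary and secondary analyses are unaffected.

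**What to change.** In the Aim 3 paragraph of Section 7.9, replace the t-tests with one of the following:
- ANCOVA for each scale: interim score on arm, the baseline score of the same scale, and the randomisation strata of Section 5.3.1 (baseline MVPA category within adolescents and within emerging adults).
- The Aim 2 baseline-constrained repeated-measures model applied to each scale, with time coded 0 for baseline and 1 for interim and the two visits allowed to correlate within participant. This also keeps participants whose interim score is missing, which is the reason the plan gives for using it in Aim 2.

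Report the adjusted arm difference with its confidence interval. For clarity, also state which baseline mechanism and baseline MVPA or SB terms enter the mediation models.

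The cost is SAP wording only. The baseline and interim questionnaires are already scheduled, so no new data, visits or participants are needed.

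### Aim 3 lets nearness to significance stand for the salience of a mechanism; with 75 to 100 participants that is a poor selector, and reporting all ten indirect effects with intervals would serve the purpose better

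*Combined protocol and SAP*

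**What the plan says.** Section 7.9 (Analysis Plan, Aim 3) plans arm comparisons of the mechanism scales at the interim assessment. These are followed by longitudinal mediation models with bootstrap tests, fitted with the mediators singly and together. It admits that the sample may be too small to detect mediation, and continues: "indirect paths nearing significance will have important implications for the future refinement of the intervention". The reason given is that such paths let the team concentrate on the most salient mechanisms for the next grant application. It then names a second input, Pearson correlations that reach significance, where the text reads: "baseline levels of proposed mechanisms of change and MVPA and SB may also be informative for adjusting the intervention prior to the R01 application".

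Aim 3 gives no cut-off for 'nearing', no alpha, no minimum effect size and no treatment of multiple tests. Section 3.2.4 lists five mechanism scales: Benefits of PA, Subjective Norms, Social Support, Barriers and Self-Efficacy. With two outcomes, MVPA and SB, that makes ten indirect paths and ten baseline correlations. Section 3.1 labels Aim 3 exploratory.

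**The concern.** A path can come near significance because it is strong, or because a weak path met a favourable sample. It can fall well short because the sample is small. Once low power is conceded, a p-value just outside the threshold says little about which mechanism matters most, yet that is the use the text gives it.

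The baseline correlations have a different weakness. They are cross-sectional and precede any coaching. They can show that active participants hold different beliefs, but not that changing the belief changes the activity.

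At stake is the content of the intervention in the next trial: effort could go to a mechanism that does nothing, or be taken from one that works. No primary or secondary result of this trial is affected.

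**Working it through.** **Inputs from the documents.** Section 5 plans "in Phase 2, 100 participants (50 participants per arm"). Phase 1 has 125. Section 7.6 predicts retention of at least 75%, so the low end is 0.75 × 100 = 75 analysed (76 where equal arms are needed). Five scales × two outcomes = 10.

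**Assumptions, not in the documents.** Two-sided alpha of 0.05; 'nearing' means p < 0.10. Here *d* is the arm difference on a scale in SD (a-path) and *b* is the standardised scale-to-outcome path.

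**1. The plan's own power figures.** Section 7.7 says n = 50 "per group will provide 80% power to detect a large effect size", "still allowing for possible detection of a medium effect size ($d=.6$) with 55% power". For two means the noncentrality is d√(n/2). At n = 50 it is 0.8 × 5 = 4.0 and 0.6 × 5 = 3.0, giving 97.7% and 84.4%. The stated 80% and 55% do not reproduce at n = 50 per group; n = 25 per group gives 79.1% and 54.7%. That is a separate matter. For this point, no power is given for any Aim 3 path, and the Section 7.7 figures cannot stand in for it.

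**2. One path tested alone, N = 100, p < 0.10.** An indirect effect a × b qualifies when both parts do, so its chance is roughly the product of the two powers. For d = 0.5, b = 0.3: 0.80 × 0.93 = 0.74. Simulation (20,000 runs):

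| Path | Missed, N = 100 | Missed, N = 76 |
|---|---|---|
| d = 0.3, b = 0.15 | 80% | 87% |
| d = 0.4, b = 0.2 | 60% | 72% |
| d = 0.5, b = 0.3 | 26% | 42% |
| d = 0.8, b = 0.3 | 9% | 18% |

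A percentile bootstrap check agreed with these to within a few percentage points.

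**3. One inert path.** With no arm difference and no outcome link, 0.10 × 0.10 = 0.01. If coaching moves the scale by d = 0.5 but the scale does not affect the outcome, 0.80 × 0.10 = 0.08. The first case is rare; the second is about eight times as frequent.

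**4. The five scales together.** Scenario: scales correlated 0.3, each moved 0.4 SD, one true mechanism with b = 0.3 on both outcomes, simultaneous model, Monte Carlo intervals for a × b. Ranges are across repeated runs.

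| | N = 100 | N = 75 or 76 |
|---|---|---|
| True mechanism qualifies for MVPA | 47–51% | 33–34% |
| True mechanism qualifies for MVPA or SB | about 61% | – |
| Any of four inert scales qualifies for MVPA or SB | 29–33% | 27–28% |
| True mechanism has the smallest p for MVPA | 68–70% | 57–61% |

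The second and third rows share the same either-outcome basis, although the third still counts four scales against one. With single-mediator models, which the plan also runs, an inert scale qualifies in 52% at N = 100, because it borrows the true mechanism's association.

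**5. Does size select better?** In a one-outcome run of the same scenario at N = 100, the true mechanism ranked first in 72% of trials by smallest p, 78% by largest indirect effect and 89% by largest b-path. The b-path's advantage is partly built in, since every scale is moved equally.

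**6. Baseline correlations.** If all ten were null and independent, 1 − 0.95¹⁰ = 0.40 is the chance of at least one significant result. With correlated scales and outcomes it is 32–37%. A correlation of 0.3 that arose only through confounding would be flagged 86% of the time at N = 100. A true correlation of 0.2 would be found 52% of the time at N = 100 and 61% at N = 125; the text does not say which sample is used.

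**The case against.** The strongest reply is that these are exploratory remarks and not decision rules. Aim 3 is labelled exploratory, low power is admitted, no cut-off or rule for dropping content is given, and Section 7.7 makes effect estimation the main goal and advises caution. The arm comparisons at the interim assessment already examine whether coaching moved each scale. Focus groups and satisfaction ratings also feed refinement. All of that stands, and it keeps the point minor. It does not make near-significance a sound guide to salience, which is the use the text states.

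Four stronger readings are tempting and should not be made.

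- *That the intervention will be changed on the baseline correlations.* The text says only that they may be informative.
- *That with ten paths some will come near significance by chance.* An indirect effect needs both parts. With neither present the rate is about 1% per path, or 10 × 0.01 = 0.1 expected among ten. The risk comes from coaching moving scales that do not drive activity, not from the count.
- *That the rule usually picks the wrong mechanism.* In the scenario above the true one has the smallest p in about 70% of trials at N = 100, against 20% by chance, and most trials select no inert scale. Large paths (d = 0.8, b = 0.3) are mostly found.
- *That significance ignores size and uncertainty.* It reflects both, but merges them into one number. At N = 100 a significant correlation is simply one above about 0.20 in absolute value.

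**Conclusion.** The point holds as a minor improvement to an exploratory aim. 'Nearing significance' is undefined and is a poor measure of salience with 75 to 100 participants. Under the stated scenario at N = 100, the true mechanism qualifies for MVPA about half the time (about 61% for either outcome), and at least one inert scale qualifies for either outcome in about 30% of trials.

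These figures rest on assumed path sizes, an assumed correlation among scales and an assumed p < 0.10. The inert figure further requires that coaching move scales that do not drive activity. That is plausible, because the sessions in Section 5.4 target all three constructs, but the documents do not establish it. The case against using baseline correlations as evidence of mechanism needs no simulation: it follows from their being cross-sectional. The 32–40% false-positive range assumes that all ten are null.

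**What to change.** In Section 7.9, Aim 3:

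- Replace the sentence on near-significant paths with a commitment to report all ten standardised indirect effects (five scales × MVPA and SB), with their a- and b-paths and 95% bootstrap intervals, whatever the p-value.
- State that refinement will weigh the size and interval of the a-path (did coaching move the scale) and the b-path (does the scale relate to the outcome), and not closeness to a significance threshold.
- Label the baseline correlations descriptive and not evidence of mechanism.

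A multiplicity correction is not a good substitute. Testing at 0.05 / 10 = 0.005 cuts the chance of any false correlation from 40% to 4.9%, but power for r = 0.3 at N = 100 falls from 86% to 60%, and power for a path with d = 0.5, b = 0.3 falls to about 22%.

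The cost is wording and slightly more reporting; models and software are unchanged. The intervals will be wide. At N = 100 an indirect effect of 0.4 × 0.2 = 0.08 SD has a 95% sampling range of about −0.01 to 0.22, against −0.11 to 0.11 for an inert scale moved by 0.5 SD. These overlap heavily, and the report should show that openly.

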Two studies have reported time spent in MVPA among adolescents with CHD as measured by accelerometer. Duppen and colleagues (2015)²⁷ stated that only 30% of their sample did not meet guidelines for MVPA (>60 min/day), which contrasts a study by Morrison et al. (2013)²⁸ in which adolescents averaged 29 min/day in MVPA. Duppen et al.,²⁷ noted that cultural and

geographic differences may explain discrepancies within the literature, further highlighting the importance of identifying rates of MVPA among adolescents in the U.S., of which the literature is completely lacking. Only 27% of “healthy” U.S. adolescents from the general population report any form of daily PA,²⁹ suggesting that a large portion of adolescent CHD survivors in the U.S. are also relatively inactive, despite being at greater risk for poor health outcomes. A similar picture emerges from studies on adult CHD survivors. Dua et al. (2007) documented that among young adult (age 31.7±11.0) CHD survivors in the United Kingdom, only 23% who reported no functional impairments met national guidelines of at least 30 min/day of moderate intensity PA.³⁰ Sandberg et al. (2016) found that only 50% of Swedish adult CHD survivors (age was undefined) met the World Health Organization’s recommendations for PA, which was true for both CHD survivors and age- and sex-matched controls.³¹ McKillop et al. (2018) reported similar averages for min spent in MVPA, as did Dua and colleagues (26 min) on a small Canadian sample of 15 emerging adults.³² Only 21% of U.S. adults from the general population meet the Centers for Disease Control and Prevention guidelines of at least 150 min/week of moderate intensity aerobic activity.²⁹ This suggests that a large portion of adult CHD survivors in the U.S. are also likely to be relatively inactive, despite being at greater risk for poor health outcomes.

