4 STUDY DESIGN

This single-site study is a randomized clinical trial of a Fitbit and exercise prescription vs. a Fitbit, exercise prescription, AND videoconferencing sessions with a PA coach over the course of 8 sessions in 20 weeks.

For Phase 1, participants are asked to complete less than 30-45 minutes of questionnaires wear an accelerometer for 7 days, and undergo an exercise stress test. For adolescent participants, a caregiver is asked to complete 20-30 minutes of questionnaires. Once the exercise stress test is completed and the accelerometer is returned, participants are compensated \$100. Once caregivers complete the online questionnaires, they are compensated \$20. Parking and mileage reimbursement to/from the hospital is provided.

If a participant engages in less than 60 minutes of MVPA per day and has no contraindications on the exercise stress test, he/she is approached for participation in Phase 2. Once recruited, participants receive a Fitbit and an explanation of their exercise prescription based on the results of their exercise stress test as provided by an exercise physiologist. Next, study staff open an envelope (pre-prepared by the study statistician, [name]) to reveal the participant's study arm designation.

Participants are randomized to 1 of 2 arms: the comparison arm, which receives a Fitbit and the exercise prescription, or the intervention arm, which also receives a Fitbit and exercise prescription PLUS videoconferencing sessions (e.g., FaceTime, Google Hangouts or Skype) with a PA coach (8 sessions over the course of 20 weeks). Each session lasts approximately 30 minutes and is audiotaped. The intervention arm focuses on changing attitudes (e.g., identifying pleasurable physical activities), perceptions of social norms of PA (e.g., problem-solving ways to receive support from family and friends) and perceptions of control for engaging in PA (e.g., increasing self-efficacy through goal setting and reducing barriers), as outlined by the Theory of Planned Behavior, to increase time spent in MVPA and decrease SB. The Fitbit is used to facilitate goal setting and self-monitoring for participants in the intervention arm.

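### Linear regression is the only method named for the exploratory analysis of who joins Phase 2, which on the natural reading is a yes/no outcome; a binary model should be named

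*Combined protocol and SAP*

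**What the plan says.** The passage is the Other Analyses paragraph that closes section 7.9. It is exploratory: "Relationships between other predictors and study outcomes will also be explored". The example that follows takes its predictors from three domains, namely cardiac anxiety, body image and the caregiver's views. It then gives two outcomes and one method: "willingness to participate in Phase 2 of the study, as well as change in the study outcome variables using linear regression". That is the only method in the sentence, and neither logistic regression nor any other binary-outcome model appears elsewhere in the plan.

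Willingness is not defined. The baseline questionnaires in section 6.2 include no willingness scale. The same section says that eligible participants are phoned and asked to schedule a visit if they are interested. What will be observed is therefore whether each eligible person joined or declined.

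On numbers, section 5 says: "The total target sample size for enrollment in Phase 1 is 125 participants and in Phase 2, 100 participants (50 participants per arm"). It attributes the difference to some participants proving ineligible. Section 7.6 adds that "recruitment and retention rates are predicted to be" at least 75%, without a separate figure for Phase 2 uptake among those eligible.

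On covariates, section 7.9 says: "Only the pre-specified covariates of baseline minutes spent in MVPA and baseline VO_{2max} will be included in the primary analyses". For Other Analyses it says nothing about the outcome's baseline value or about study arm.

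**The concern.** A straight line fitted to a 0/1 outcome has two known weaknesses when most people say yes. Its fitted values can exceed 1, and the outcome variance p(1 - p) changes with the predictor, so the usual standard errors can be too small or too large. High Phase 2 uptake is plausible here, and scores for cardiac anxiety, body image disturbance and caregiver perceptions may well be skewed.

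The stakes are limited but practical. This is a pilot meant to inform a larger trial, and a profile of who declines is useful for planning its recruitment. Predicted uptake above 100%, or an interval with the wrong coverage, would weaken that use.

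**Working it through.** The plan gives no figure for this analysis, so there is none to reproduce. The uptake rates, slopes, correlations and the SD of MVPA below are assumptions; the documents state none of them.

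**1. How many decliners?** Let I be the ineligible and D the eligible decliners. If both targets in section 5 are met exactly, 125 - I - D = 100, so D = 25 - I. Uptake among the eligible is 100/(100 + D).

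- D = 25 gives 100/125 = 80%, but only if nobody is ineligible.
- D = 11 gives 100/111 = 90%.
- D = 5 gives 100/105 = 95%.

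The documents do not fix I, so D is unknown. Section 5 points to I as the reason for the gap.

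**2. Where does a linear fit pass 1?** Near mean uptake p, a log-odds slope b per SD corresponds to a linear slope of about b·p(1 - p). The line reaches 1 at (1 - p)/[b·p(1 - p)] = 1/(b·p) SD above the mean. With b = 0.7:

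- p = 0.80: 1/0.56 = 1.79 SD
- p = 0.90: 1/0.63 = 1.59 SD
- p = 0.95: 1/0.665 = 1.50 SD

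For a normal predictor about 3.7% of people lie beyond 1.79 SD. That is 125 × 0.037 = 4.6 people in a sample of 125.

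**3. Simulation, normal predictor, n = 125, two-sided 0.05, 2,000 datasets per row.**

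| Assumed uptake | False positives, linear | False positives, logistic | Power at b = 0.7, linear | Power at b = 0.7, logistic | Any fitted value > 1 at b = 0.7 |
|---|---|---|---|---|---|
| 80% | 4.3% | 4.0% | 85% | 85% | 75% |
| 90% | 4.0% | 3.5% | 67% | 65% | 79% |
| 95% | 5.5% | 4.4% | 44% | 41% | 77% |

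**4. Smaller samples and skewed predictors.** A second simulation used n = 70-110, uptake 75-90% and b = 0.7. The linear model's false-positive rate was again near 5%. With the non-zero slope, fitted values above 1 occurred in 60-83% of datasets in most settings and in 4-10% in the two lowest. With a skewed predictor, coverage of nominal 95% intervals ranged from 85% to 99%, and power differed from that of logistic regression.

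**5. The change models.** Linear regression suits a continuous change. The open question is whether the outcome's baseline value enters. It was checked with n = 100 and arm in the model. Baseline MVPA had mean 29 min/day (section 2.1 cites a study "in which adolescents averaged 29 min/day in MVPA"; 45 was also tried in the first row below), assumed SD 15 and assumed reliability 0.5-0.7. Entry followed section 4 ("If a participant engages in less than 60 minutes of MVPA per day"). Rejection rates for the predictor:

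| Predictor related to | Baseline not in model | Baseline in model |
|---|---|---|
| Stable activity level only (correlation 0.4) | 5-9% | 31-40% |
| Observed baseline (correlation 0.3-0.4) | 18-45% | 4-6% |
| Transient baseline variation only (correlation 0.4) | 80% | 40-59% |
| Neither | 5% | 5% |

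Neither model is right in every row.

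**The case against.** **The sentence is ambiguous.** The reference to linear regression may attach only to outcome change, for which it is appropriate. This is a fair reading, but uptake then has no stated method, and the same one-line addition is needed.

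**The test is hardly affected.** This stands. False-positive rates are 4.0-5.5%, and with a normal predictor the power is close to that of logistic regression. Someone who wants only a p-value for a possible predictor loses little. What remains is the effect scale, predictions above 1, and interval coverage with skewed predictors.

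**The analysis is exploratory.** This also stands. No primary or secondary efficacy test, sample size or decision rests on it.

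Two stronger readings are tempting and are not supported:

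- A reader might infer from 100 of 125 an uptake of 80% with about 25 decliners. Section 5 gives ineligibility as the reason for that gap, so the figure is neither an uptake rate nor a count of people who said no.
- A reader might infer that the change models omit the baseline value, so that regression to the mean will produce false predictors of change. The plan does not say the baseline value is omitted. Section 2.1 says in general terms that objective MVPA measures will be covariates in the study analyses, although section 7.9 names them only for the primary ones. The inflation also depends on how the predictor relates to baseline. Where it tracks only stable activity, adjusting for baseline raises rejection instead of lowering it.

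**Conclusion.** The point holds for uptake only, and it is minor. On the natural reading, a joined/declined outcome has linear regression as its only named method. On the other reading it has none.

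Given a real association, fitted probabilities above 1 are usual (75-79% of datasets with 125 participants). Coverage of nominal 95% intervals can run from 85% to 99% when the predictor is skewed. The false-positive rate stays near 5%. These sizes rest on an assumed log-odds slope of 0.7 per SD and assumed uptake of 75-95%. Lower uptake or weaker predictors would shrink them.

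Linear regression for continuous outcome change is sound. Whether to include the outcome's baseline value is a choice between two questions: what predicts change, and what predicts the final level among people with the same baseline. Leaving that open in an exploratory paragraph is not an error.

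**What to change.** Add one sentence to Other Analyses in section 7.9. Define Phase 2 uptake as enrolled versus declined among Phase 1 participants who are eligible and approached, and analyse it by logistic regression. Use a penalised (for example Firth) likelihood if decliners are few, since their number is not stated and may be small. Keep linear regression for continuous outcome change.

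The sentence should also note that caregiver predictors exist only for adolescents. Those uptake models can therefore use at most the 85 adolescents planned for Phase 1, less any who are ineligible.

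It would help, though it is optional, to say whether the change models include the outcome's baseline value and arm, and which question that answers.

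The cost is wording only. No new data, visits or participants are needed, and the efficacy analyses do not change.
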